Combined stimulation of the NO-cGMP and PGI2-cAMP systems potentially maximises the above benefits, if it does not increase adverse effects, so cilostazol and ISMN together may be more effective than either drug alone. Both may improve BP control, lower BP modestly, reduce BP variability, further reducing stroke and SVD risk. Combining ISMN (no antiplatelet effects) and cilostazol (weak antiplatelet) should avoid excess bleeding when given with guideline clopidogrel or aspirin (both moderate-strong antiplatelet agents).³³

Rationale for the approach: The trial was designed as part of an NIHR SRN-Portfolio Development Expert Writing Group using experience from the USA NIH-funded SPS3 trial (3000+ lacunar stroke patients, CI [name]; SRN Writing Group, Laci-2 International Advisor to TSC),^{33, 35, 36} the CSPS and CSPS2 trials (3740 patients^{44, 46}) and ongoing CSPS3 trial testing cilostazol to prevent stroke in Japan (PI [name], International Advisor to TSC), the PRESERVE trial (CI [name], SRN Writing Group), and in monogenic SVD ([name], SRN Writing Group, International Advisor to TSC). UKSRN Prevention CSG strongly supported a trial testing cilostazol and ISMN in SVD prevention: many (>80) UK Stroke Research Network Centres expressed interest in joining the trial.

Relevant drugs are available: Although many experts are uncertain of what agents to test in lacunar stroke,^{33,35} we identified targets with available drugs.^{10,16,41} Other trials are testing BP-lowering on cognition in patients with combined lacunar stroke and severe WMH (BHF PRESERVE, CI [name], UK). However, other approaches are clearly needed since hypertension explains <1.5% of variance in WMH,¹⁸ target BP reduction did not prevent stroke or cognitive decline in SPS3,³⁵ may increase stroke⁵⁸ and SVD worsening at older ages.⁵⁹ There is increasing uncertainty about antiplatelet drugs: in SPS3, they increased hazard without benefit.^{33,37} SVD is now recognised as a major cause of haemorrhagic stroke⁶⁰ especially at older ages.

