9.2 PROPOSED ANALYSES

We will compare cilostazol v no cilostazol, ISMN v no ISMN, cilostazol and ISMN v neither. The proportion completing to target dose and any adverse events will be assessed using odds ratios. The LACI-2 will focus on numbers recruited, retained, tolerance and safety outcomes, blinded for TSC and unblinded intention to treat (ITT) for DMC. Safety analysis will use: Kaplan-Meier and Cox proportional regression for analysis of time-to-event outcomes of death; binary logistic regression for SAEs, recurrent stroke, MI, and in those completing 12 month MRI, the amount of microbleeds, siderosis, new infarcts, WMH burden; all adjusted for minimisation variables to maximise power.⁶⁷ We will collect data for future health economics analysis (EQ-5D-5L, EQ-VAS).

A secondary ITT analysis will be performed using logistic regression adjusted for minimisation variables of cilostazol+/-ISMN versus control on efficacy and safety outcomes, with secondary tests of subgroup interactions. Ordinal logistic regression will be used for ordinal categorical outcomes (e.g. mRS) to increase power.⁶⁸

A Statistical Analysis Plan (SAP) will be published prior to database lock and will describe analysis procedures and procedures for missing, unused or spurious data, and definitions of populations analysed.

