- Death, including fatal haemorrhage, aiming for less than outside the upper 95% CI of 2% per year.
- The *combined rate* of recurrent stroke, MI, death, cognitive impairment and dependency, aiming for 40-50% at one year after enrolment.

Comparison of rates of events between the treatment groups: cilostazol vs no cilostazol, ISMN vs no ISMN, and cilostazol and ISMN vs neither, for:

- Systemic or intracranial bleeding, recurrent cerebral and systemic vascular events, and vascular and non-vascular causes of death.
- Death, all cause.
- New ischaemic or haemorrhagic stroke lesion or increase in SVD lesions on MRI.
- Composite of: recurrent clinically-evident stroke, MI, death, cognitive impairment (including dementia) and dependency.
- Individual event: stroke (clinically-evident or imaging-detected ischaemic or haemorrhagic stroke to be reported separately), TIA, myocardial ischaemia, cognitive impairment and dementia.
- New infarcts and haemorrhages, absolute and change in WMH, microhaemorrhages, lacunes, atrophy imaging variables from central read of baseline imaging and one year MRI
- The comparisons of combined cilostazol and ISMN versus neither, whilst being very underpowered statistically, are presented since these may be the two groups studied in the planned follow-on trial.

Central tendency, comparisons and regressions will be analysed as follows (**Table D**).

Table D. Descriptive and analytical statistics

	Binary	Nominal	Ordinal	Continuous
Central tendency and distribution	N (%)	N (%)	Median [interquartile range]	Mean (standard deviation)
Comparisons	Chi-square (2x2)	Chi-square (2x2, or rxc)	Mann-Whitney U or Kruskal-Wallis	t-test (pooled) or 1-way ANOVA
Regression	Binary logistic regression (BLR)	-	Ordinal logistic regression (OLR)	Multiple linear regression (MLR)

27b Covariate adjustment: Analyses will be adjusted for minimisation covariates:

- Age, sex, stroke severity (NIHSS), dependency resulting from the stroke, systolic blood pressure, smoking status, time after stroke, years of education.

Covariate adjustment with continuous variables (age, NIHSS, SBP, time after stroke, years of education) will use original, not dichotomised, data.

27c Assumption checking: The assumption of proportionality will be tested using the likelihood test.

27d Alternative methods: If the data fail the assumption of proportionality (tested using the likelihood test), we will use alternative methods such as multiple logistic regression.

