27e Sensitivity analyses: In addition to assessment of raw data, the primary outcome will be analysed using additional statistical approaches in sensitivity analyses:

- Unadjusted analysis
- Imputation (multiple regression imputation) of missing data (adjusted)¹⁶

27f Subgroup analyses: The secondary endpoint of the composite of: recurrent stroke, MI, death, cognitive impairment and dependency, will be studied in:

- Pre-specified subgroups comprising the minimisation variables.
- Any other variables demonstrating imbalance at baseline.

The results of these subgroup analyses will not be adjusted for multiple testing. These analyses are planned for the phase III efficacy trial and so will be tested in the present study.

28 Missing data

Missing data may occur at outcome level or at test level or within a test at component item level. Notably, some tests have to exclude components if performed by telephone and/or postal questionnaire or require a one year MRI. There is often a relationship between inability to complete outcome assessment and cognitive function or neurological deficit after stroke (e.g. inability to hold a pen) and so assumptions around random missingness may not be valid, even if the patterns of missing data initially suggest 'missing completely at random' status. Indeed, failure to complete a test may be an indicator of cognitive impairment rather than real missingness.

The approaches taken to missing cognitive and other data can have a substantial effect on epidemiological estimates.¹⁶ We will use the approach that makes greatest use of available data.

Where in study data are not available, or participants are lost to follow-up, we have permissions to allow for linkage of the study dataset to primary and secondary care electronic health records. This will allow for an assessment of clinical outcomes across all the participants.

29 Additional analyses

Global outcomes

We will assess global outcomes integrating multiple scores into one analysis and so provide a more holistic measure and improve statistical power. We will assess global outcomes comprising:

- Recurrent ordinal stroke (clinically-evident and/or imaging-detected),¹⁷ ordinal MI, cognition (MoCA), dependency (mRS), quality of life (EQ-5D).

Analyses will use the Wei-Lachin test¹⁸⁻²¹ with comparison of data at 1 year.

Cognitive domains, based on DSM-V

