Myocardial infarction		XX (X)
Cognitive impairment		XX (X)
Dependency, mRS>2		XX (X)
Any of these	40-50%	XX (X)

Table 3. Clinical Outcomes at 12 months.

Data are number (%), median [interquartile range] or mean (standard deviation). Analyses performed using binary logistic regression (BLR), ordinal logistic regression (OLR) or multiple linear regression (MLR) with adjustment for age, sex, time from stroke onset to randomisation, years of education, smoking status, and baseline mRS (dependency), stroke severity (NIHSS) and systolic blood pressure. Mean (SD) and MLR will be used instead of median [IQR] and OLR for ordinal scales with more than 7 levels (central limit theorem/large sample). The Wei-Lachin test is used to analyse multiple outcomes in parallel.

Number	ISMN	No ISMN	Difference (p)	Cilostazol	No cilostazol	Difference (p)	ISMN + Cil	Neither	Difference (p)
Composite									
Stroke	XX (X)	XX (X)	CPHR BLR	XX (X)	XX (X)	CPHR BLR	XX (X)	XX (X)	CPHR BLR
TIA	XX (X)	XX (X)	BLR	XX (X)	XX (X)	BLR	XX (X)	XX (X)	BLR
MI	XX (X)	XX (X)	BLR	XX (X)	XX (X)	BLR	XX (X)	XX (X)	BLR
Cognitive impairment	XX (X)	XX (X)	BLR	XX (X)	XX (X)	BLR	XX (X)	XX (X)	BLR
Dependency, mRS>2	XX (X)	XX (X)	BLR	XX (X)	XX (X)	BLR	XX (X)	XX (X)	BLR
Death	XX (X)	XX (X)	BLR	XX (X)	XX (X)	BLR	XX (X)	XX (X)	BLR
Cognition									
Cognition, 7 level Normal	XX (X)	XX (X)	OLR	XX (X)	XX (X)	OLR	XX (X)	XX (X)	OLR
Minor, single domain	XX (X)	XX (X)		XX (X)	XX (X)		XX (X)	XX (X)	
Minor, multi-domain	XX (X)	XX (X)		XX (X)	XX (X)		XX (X)	XX (X)	
Major, mild	XX (X)	XX (X)		XX (X)	XX (X)		XX (X)	XX (X)	

LACI-2 SAP V1.5

06/06/2022

Major, moderate	XX (X)	XX (X)					
Major, severe	XX (X)	XX (X)					
Death	XX (X)	XX (X)					
Cognition, 4 level							
Normal	XX (X)	XX (X)					
Minor	XX (X)	XX (X)					
Dementia	XX (X)	XX (X)					
Death	XX (X)	XX (X)					
Memory/thinking problem	XX (X)	XX (X)	BLR	XX (X)	XX (X)	BLR	XX (X)
MoCA	XX (X)	XX (X)	MLR	XX (X)	XX (X)	MLR	XX (X)
TICS-m	XX (X)	XX (X)	MLR	XX (X)	XX (X)	MLR	XX (X)
Verbal fluency, animal naming	XX (X)	XX (X)	MLR	XX (X)	XX (X)	MLR	XX (X)
Trails B, time	XX (X)	XX (X)	MLR	XX (X)	XX (X)	MLR	XX (X)
Trails B, points	XX (X)	XX (X)	MLR	XX (X)	XX (X)	MLR	XX (X)
Dementia, clinical diagnosis	XX (X)	XX (X)	BLR	XX (X)	XX (X)	BLR	XX (X)
Clinical							
Systolic BP (mmHg)	XX (X)	XX (X)	MLR	XX (X)	XX (X)	MLR	XX (X)
Diastolic BP (mmHg)	XX (X)	XX (X)	MLR	XX (X)	XX (X)	MLR	XX (X)

LACI-2 SAP V1.5

06/06/2022

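### The three planned treatment contrasts cannot separate an effect confined to the combination from independent effects of cilostazol and ISMN; add an exploratory interaction estimate for the composite and four-cell results

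*SAP*

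**What the plan says.** SAP section 27a lists the comparisons as "cilostazol vs no cilostazol, ISMN vs no ISMN, and cilostazol and ISMN vs neither", and protocol section 9.2 lists the same three. On the third the SAP is candid: "The comparisons of combined cilostazol and ISMN versus neither, whilst being very underpowered statistically, are presented" because "these may be the two groups studied in the planned follow-on trial".

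Section 27b adjusts for the minimisation variables: "Age, sex, stroke severity (NIHSS), dependency resulting from the stroke, systolic blood pressure, smoking status, time after stroke, years of education". The Table 3 heading gives the same set, "with adjustment for age, sex, time from stroke onset to randomisation, years of education, smoking status" and so on. The other trial drug is in neither list.

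The planned interaction tests concern baseline factors. SAP section 27f names "Pre-specified subgroups comprising the minimisation variables" plus any variables imbalanced at baseline, and protocol section 9.2 speaks of secondary ITT analyses "with secondary tests of subgroup interactions". No forest plot in Figures 2 to 4 has a row for the other drug.

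Tables 3, 7a–c, 8 and 9 show each drug's margin and both versus neither, without ISMN-only or cilostazol-only columns. All four groups appear for baseline data (Tables 1 and 5) and adherence (Table 4). Table 2 splits tolerability into each drug alone and both.

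Protocol section 3 says the partial factorial design permits testing the drugs singly and in combination. It also lets a patient with a contraindication to one drug enter the other drug's comparison only. Protocol section 1.2 reasons that the two pathways may complement each other, "so cilostazol and ISMN together may be more effective than either drug alone", provided adverse effects do not increase.

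**The concern.** A marginal comparison in a factorial trial averages a drug's effect over the presence and absence of the other drug. If the drugs do not interact, that average is also the effect of the drug given by itself. If they do, it mixes two different effects. The protocol treats how the drugs behave together as open, and section 1.2 says it is not known whether both can be taken together in full dose.

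The SAP has no analysis that compares the combination with what the single drugs would predict. What is at stake is what LACI-2 can tell the planners of the next trial: whether any signal on the composite comes from one drug, from each independently, or only from the pair. The data to describe this are being collected, but no estimate of it is planned.

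**Working it through.** **Inputs.** Control composite rate 45% and active rate 36% (model D: protocol Table 7, SAP Table B); 363 patients recruited (SAP Table 2); death 2% a year and non-fatal ICH 0.5% a year (SAP section 11a and Table A). Assumptions: four equal cells, complete outcomes, and the cell risks below. The documents give no cell sizes.

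**The plan's own figure.** With z-values for two-sided 5% and 80% power, n per group is [1.96·√(2 × 0.405 × 0.595) + 0.842·√(0.45 × 0.55 + 0.36 × 0.64)]² / 0.09² ≈ 466. The Fleiss correction gives (466/4)·[1 + √(1 + 4/(466 × 0.09))]² ≈ 488, so 976 in total, as stated. 976/0.9 = 1085 against the stated 1100. The documents give no sample size or power for an interaction.

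**Why the third contrast adds nothing.** Write the risks as p00 (neither), p10 (cilostazol only), p01 (ISMN only) and p11 (both).
- Cilostazol margin: (p10 + p11)/2 − (p00 + p01)/2
- ISMN margin: (p01 + p11)/2 − (p00 + p10)/2
- Their sum: p11 − p00, which is both versus neither.

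**Two scenarios**

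| | Combination only | Independent effects |
|---|---|---|
| p00 / p10 / p01 / p11 | 45 / 45 / 45 / 36% | 45 / 40.5 / 40.5 / 36% |
| Each margin | 40.5% v 45% | 38.25% v 42.75% |
| Marginal risk difference | −4.5 points | −4.5 points |
| Marginal OR | 0.83 | 0.83 |
| Both v neither | −9 points, OR 0.69 | −9 points, OR 0.69 |
| Interaction ratio of ORs | 0.69 | 0.99 |

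The three planned contrasts agree; only the last row separates the scenarios. In the first, each margin shows half the combination's risk difference.

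**Would adding the other drug as a covariate help?** In the combination-only scenario the effect of cilostazol is 0 without ISMN (45 v 45) and −9 with it (36 v 45). The average is −4.5, the same as the crude margin. A main-effect covariate does not reveal the difference.

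**Precision of the interaction, composite.** With a common rate of 45%:
- Main-effect SE of the log OR: 2/√(363 × 0.45 × 0.55) = 0.211, so the CI factor is exp(1.96 × 0.211) = 1.5.
- Interaction SE: 4/√(363 × 0.45 × 0.55) = 0.422, so the factor is exp(1.96 × 0.422) = 2.3.
- At an assumed 300 patients the factor is 2.5; at an assumed 250 it is 2.7.

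With the combination cell at 36%, the SE is √[3/(90.75 × 0.45 × 0.55) + 1/(90.75 × 0.36 × 0.64)] = 0.43. The interaction ratio of 0.69 then has a 95% CI of about 0.30 to 1.58 and power of about 14%. Power is about 27% with that cell at 31.5%. For 80% power at a ratio of 0.69, about 3,680 patients are needed.

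**Sparse outcomes.** Deaths: 363 × 0.02 ≈ 7. With 91 per cell, the chance of no deaths in a given cell is 0.98⁹¹ ≈ 0.16, so at least one cell is empty with probability 1 − 0.84⁴ ≈ 0.50. Non-fatal ICH: 363 × 0.005 ≈ 2 events across four cells. No overall bleeding rate is given.

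**The case against.** The strongest reply is that this is a feasibility trial with little power for any interaction, that both versus neither is the only contrast the SAP links to the next trial, and that this contrast is valid whether or not the drugs interact. All of that stands. It rules out a significance gate, and it means that the documents do not make the choice of phase III arms depend on the interaction; protocol sections 1.2 and 2.1 tie progression to procedures, event rates and recruitment. It does not rule out an estimate. The SAP already presents one contrast that it calls very underpowered because it may inform the follow-on trial, and the same reasoning applies here.

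A reader could also recover crude single-drug counts by subtracting the combination column from each margin in Table 3. That works if denominators line up, which partial entry makes uncertain, and it gives no adjusted estimate or interval.

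Several stronger readings are tempting, and the documents do not support them:
- *That the SAP would report a combination effect as the effect of each drug alone.* Its labels are marginal (drug versus no drug), and a marginal effect is a valid randomised estimand.
- *That leaving the other drug out of the models causes the problem.* It does not, as shown above.
- *That each drug would then look active.* With a combination OR of 0.6 and inactive single drugs, the marginal OR is 0.78 with SE 0.211, so the expected 95% CI is about 0.52 to 1.18, usually inconclusive.
- *That the protocol asserts synergy.* Being more effective together than either alone is equally consistent with simple additivity.
- *That tolerability needs the same treatment.* It is already split by arm, and tolerability of a trial drug is undefined in patients allocated to neither.

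**Conclusion.** The gap is real but limited. For efficacy and safety outcomes, the three planned contrasts cannot tell a combination-only effect from two independent effects, and no planned table shows the single-drug cells. The identity behind this is exact for risk differences in a balanced 2x2. In the example the odds ratios agree to two decimals.

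The consequence is an interpretive gap for phase III planning; the planned estimates remain valid. The primary feasibility endpoint is untouched.

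An interaction estimate for the composite is feasible but imprecise. The factor of x/÷ 2.3 assumes 363 complete outcomes in equal cells at a 45% rate. Partial-factorial entry and missing outcomes will make it wider, and 2.5 or 2.7 are illustrations at assumed totals. A fitted interaction is not workable for death, and should not be attempted for bleeding, where events are expected to be sparse. This is a cheap improvement that should be made.

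**What to change.** 1. **Composite.** Using the composite as listed in SAP section 27a, and only patients randomised for both drugs, fit one model with cilostazol, ISMN and their product, plus the section 27b covariates. Report the ratio of odds ratios with its 95% CI, labelled exploratory. Draw no conclusion from its p value and let it gate no other analysis. State how many patients were randomised for both drugs.
2. **Four cells.** Add ISMN-only and cilostazol-only columns to the composite rows of Table 3. For death and bleeding, show counts and percentages in all four cells without a fitted interaction.
3. **No change** to tolerability and adherence, which Tables 2 and 4 already split by arm.
4. **Separate minor point.** Include the other drug's allocation as a covariate in each marginal model, and say how patients who entered only one comparison are handled. This does not resolve the question of interaction.

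Cost: a few lines of SAP wording, one extra row for the composite and two extra columns, all from data already collected. Downside: a wide interval will be shown, and the text should say plainly that it neither establishes nor excludes an interaction.
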